4.5.3 Treatment Interruptions

Study medication will be interrupted for ANY of the following reasons:

Infection, fever, or decrease in ANC:

- If the patient develops an infection during the study, deferiprone must be interrupted immediately and neutrophil count should be obtained and monitored more frequently (every 2 days if ANC <1.5 x 10⁹/L). Patients should be advised to report immediately to their physician any symptoms indicative of infection such as fever, sore throat, and flu-like symptoms. They will be provided with a thermometer, and instructed to seek immediate medical attention at a hospital or clinic if they experience fever (temperature >38.0° C/100.4°F). Body temperature may be measured at the mouth, axilla, or ear. Patients/legal guardians will be provided with an emergency services card with contact information, and will be advised to carry this card at all times. In presence of confirmed fever and/or infection, they will be required to have their neutrophil counts tested as soon as possible and no later than 24 hours after the symptoms of infection are detected. Therapy with deferiprone can be re-initiated once all symptoms have been resolved and it is deemed safe by the investigator.
- If temperature is >38.0°C/100.4°F and ANC is \le 0.5 x 10⁹/L, the following must be done:
 - Commence therapy with antibiotics immediately (treatment should depend on the site of the suspected infection and on local antibiotic policy)
 - Perform a chest x-ray, and collect blood and other relevant cultures (if possible, collect culture samples before initiating antibiotics)

• If the patient develops moderate neutropenia while on deferiprone, therapy must be interrupted immediately and neutrophil count must be obtained and monitored every 2 days. Therapy with deferiprone can be re-initiated once two successive ANCs are >1.5 x 10⁹/L and it is deemed safe by the investigator. The patient will be withdrawn from the study if the ANC remains <1.5 x 10⁹/L by the end of a 2-week period (14 days).

For definitions of and further detail on the management of neutropenia, see Section 7.2.1.8.1.

Increase in ALT:

If a patient whose ALT level was normal at baseline is confirmed to have serum ALT levels $\geq 5 \text{ x ULN}$ on 2 consecutive assessments, deferiprone treatment may be interrupted based on investigator judgment.

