 - To interrupt therapy immediately if an infection develops, and to immediately report any symptoms indicative of infection such as fever, sore throat, or flu-like symptoms. In presence of confirmed fever and/or infection, they will be required to have their neutrophil counts tested as soon as possible and no later than 24 hours after the symptoms of infection are detected.
 - o If patient decides to leave the study before completion, to return to the clinic for an Early Termination Visit as soon as possible, and no later than 1 month following the last dose of study medication
- Provide patient or authorized legal representative with an emergency card, and advise her/him to carry this card at all times
- Schedule next study visit

Regular Blood Draws

Notes:

- o These blood draws can be conducted either at a local laboratory or at the study site.
- o For patients in Group 1, the blood draws will be done monthly. For patients in Group 2, they will be done weekly for the first 6 months (up to Week 26), biweekly for the next 6 months (up to Week 52), and monthly thereafter. In all cases, the window is \pm 3 days.
- Collect blood sample for hematology. Hematology results should be reviewed by the investigator as soon as they are received from the laboratory (within 24 hours if possible).
- If the patient receives a blood transfusion (either at one of these visits or at any other time during the study), record the type of transfusion (simple, exchange, partial

exchange; and if exchange or partial exchange, what was the volume of blood removed and the average mean hematocrit of the packed red blood cells removed), volume of blood that the patient received during the transfusions, and the mean hematocrit of the packed red blood cell units transfused (data obtained from the site's blood bank).

Visit 2 (Week 13 ± 7 days)

- Review patient diary card, and file it with the source documents
- Document information on adverse events, use of concomitant medications, and treatment compliance
- Collect blood samples for the following assessments:
 - Hematology
 - Serum ferritin

Pregnancy

- o testing for all females of childbearing potential. A negative result is required for study continuation.
- Measure vital signs and weight

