7.2.1.8 Adverse Events of Special Interest

7.2.1.8.1 Neutropenia

Patients taking deferiprone must be monitored for neutropenia, defined as a confirmed absolute neutrophil count (ANC) less than 1.5×10^9 /L. Categories of neutropenia are as follows:

• Mild: A confirmed ANC $< 1.5 \times 10^9/L \text{ but } \ge 1.0 \times 10^9/L$

• Moderate: A confirmed ANC $< 1.0 \times 10^9/L \text{ but} \ge 0.5 \times 10^9/L$

• Severe: A confirmed ANC $< 0.5 \times 10^9$ /L. Severe neutropenia is also

referred to as agranulocytosis.

For a case of neutropenia to be confirmed, there must be 2 consecutive counts, a maximum of 3 days apart, that are both less than the specified value. If both counts are below 1.5×10^9 /L but are not in the same severity category, a third count will be required to determine the severity.

The management of different severities of neutropenia is described below. In addition to having ANC monitored, patients or authorized legal guardians will be advised to immediately report any symptoms indicative of infection such as fever, sore throat, and flulike symptoms; and will be provided with an emergency services card with contact information which they are advised to carry with them at all times. In presence of confirmed fever and/or infection, they will be required to have their neutrophil counts tested as soon as possible and no later than 24 hours after the symptoms of infection are detected.

Mild neutropenia: The patient should continue deferiprone treatment, and ANC will be monitored every 2 days until resolution of the event, defined as 2 consecutive ANC ≥ 1.5 x 10^9 /L. If ANC is still < 1.5 x 10^9 /L after 14 days, the investigator is to do the following:

- Withdraw patient from the study and monitor him/her until resolution of the event
- Advise patient regarding protective isolation
- Examine patient the same day (if possible), including drug history and physical examination
- Notify ApoPharma Inc. by fax

If a patient with mild neutropenia develops an infection, deferiprone therapy must be interrupted immediately, and neutrophil count will continue to be monitored every 2 days

until resolution. Therapy can be re-initiated once all symptoms have been resolved and it is deemed safe by the investigator.

Moderate neutropenia: Patient will immediately interrupt treatment, and ANC will be monitored every 2 days until resolution of the event. If ANC is still $< 1.5 \times 10^9$ /L after 14 days, the investigator is to do the following:

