If the patient develops fever or any type of infection during the study, deferiprone must be interrupted immediately and neutrophil count should be obtained and monitored more frequently (every 2 days if ANC $<1.5 \times 10^9$ /L). Patients should be advised to report immediately to their physician any symptoms indicative of infection such as fever, sore throat, and flu-like symptoms. Patients will be provided with an emergency services card with contact information, and the patient/legal guardian will be advised to carry this card at all times. In presence of confirmed fever and/or infection, they will be required to have their neutrophil counts tested as soon as possible and no later than 24 hours after the symptoms of infection are detected. Therapy with deferiprone can be re-initiated once all symptoms have been resolved and it is deemed safe by the investigator.

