5.2.3.2 Infections

If the patient developed fever or any type of infection during the study, deferiprone was to be interrupted immediately and neutrophil count should be obtained and monitored more frequently (every 2 days if $ANC < 1.5 \times 10^9/L$). Patients should be advised to report immediately to their physician any symptoms indicative of infection such as fever, sore throat, and flu-like symptoms. Patients has been provided with an emergency services card with contact information, and the patient/legal guardian will be advised to carry this card at all times. In presence of confirmed fever and/or infection, they would be required to have their neutrophil counts tested as soon as possible and no later than 24 hours after the symptoms of infection was detected. Therapy with deferiprone could be re-initiated once all symptoms had been resolved and it was deemed safe by the investigator.

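### The Visit 1–8 reminders and the mild-neutropenia paragraph name only infection as the trigger to interrupt deferiprone, while the Infections text and the 4.5.3 sub-heading also name fever

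*Protocol*

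**What the plan says.** Protocol 5.1 repeats one reminder at every visit where drug is dispensed (Visits 1 to 8). Its stop clause reads "To interrupt therapy immediately if an infection develops, and to immediately report any symptoms indicative of infection"; fever is then listed among those symptoms. The next sentence uses fever differently, as a trigger for a blood count: "In presence of confirmed fever and/or infection, they will be required to have their neutrophil counts tested as soon as possible", with an outer limit of 24 hours.

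Protocol 7.2.1.8.1 covers mild neutropenia, a confirmed ANC of at least 1.0 but below 1.5 × 10⁹/L. The default is to stay on drug: "The patient should continue deferiprone treatment, and ANC will be monitored every 2 days until resolution of the event". The exception is "If a patient with mild neutropenia develops an infection, deferiprone therapy must be interrupted immediately".

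Two protocol texts treat fever as a reason to stop. The Infections text of 7.2.1.8 says "If the patient develops fever or any type of infection during the study, deferiprone must be interrupted immediately". Section 4.5.3 opens with "Study medication will be interrupted for ANY of the following reasons", and the sub-heading beneath is "Infection, fever, or decrease in ANC". SAP 5.2.3.2 restates the Infections text in the past tense ("If the patient developed fever or any type of infection during the study, deferiprone was to be interrupted immediately"); it reports the rule and does not add one.

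**The concern.** Protocol 1.3 calls agranulocytosis the most significant serious adverse event of deferiprone and notes post-marketing deaths. It also says that agranulocytosis can follow soon after a normal count. The section supports less frequent ANC monitoring by relying on education: patients are to stop the drug themselves at signs of infection. In this study Group 1 is counted monthly throughout, and Group 2 monthly after Week 52.

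The visit reminders are where the protocol has staff repeat that message, and their stop clause is narrower than the rationale. A patient at home may not be able to tell whether an infection is present. A temperature can be measured, and 4.5.3 supplies a thermometer for that purpose.

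Mild neutropenia matters most, because the count is already low and the standing instruction is to continue. That ambiguity reaches the site as well as the patient: an investigator could follow the specific paragraph rather than the general Infections text for a febrile patient with no identified source.

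**Working it through.** No arithmetic applies beyond a count. The check sets each interruption instruction beside the others.

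| Place | Trigger named for stopping | What is said about fever |
|---|---|---|
| Protocol 5.1, reminders at Visits 1–8 | Infection | Report at once; ANC test within 24 hours |
| Protocol 7.2.1.8.1, mild neutropenia | Infection | Not mentioned in the paragraph; the section's preceding text requires reporting and an ANC test within 24 hours |
| Protocol 4.5.3, lead sentence and sub-heading | Infection, fever or a fall in ANC | A reason to interrupt |
| Protocol 4.5.3, first bullet | Infection | Report; seek immediate care above 38.0 °C/100.4 °F; ANC test within 24 hours |
| Protocol 7.2.1.8, Infections | Fever or any infection | A reason to interrupt |
| SAP 5.2.3.2 | Fever or any infection | Restates 7.2.1.8 |
| Protocol 1.3 | Signs of infection | Not named |

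**Are fever and infection interchangeable here?** The protocol does not use them so. The Infections text and the 4.5.3 sub-heading list them as alternatives. The reminder also pairs them as alternatives for the ANC test, two clauses after naming infection alone for stopping. A careful reader of the reminder could conclude that fever means report and test, without stopping. That differs from the Infections text.

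**How many texts are affected?** The infection-only stop clause stands in eight reminders, one bullet of 4.5.3 and one paragraph of 7.2.1.8.1: 8 + 1 + 1 = 10 locations. The eight reminders share one stop clause, so there are three distinct texts. The 4.5.3 bullet sits directly under a heading that already lists fever, which leaves two texts that carry the point: the reminder and the mild-neutropenia paragraph.

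**When does the difference bite?** Follow a patient with fever and no recognised infection.

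1. Before contact, the reminder tells the patient to report the fever, and 4.5.3 adds immediate medical attention above 38.0 °C. Neither instruction to the patient says to stop the drug on fever alone.
2. After contact, the Infections text obliges the site to interrupt at once.
3. If the patient already has mild neutropenia, step 2 still applies under the Infections text, but the paragraph written for that condition says continue unless there is an infection.

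The gap is therefore mainly step 1, with a residual ambiguity at step 3.

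**The case against.** The strongest reply is that this is editorial. No text says that infection is the only trigger, and naming one trigger does not exclude another. The Infections text is unconditional, so a site that interrupts for fever complies with every passage at once. Section 4.5.3, read as a unit, lists fever under its heading and allows restart once symptoms have resolved, which fits with the drug being off during fever. The mild-neutropenia paragraph belongs to the same section as the Infections text, does not address fever without infection, and can be read as supplemented by it; those patients are also counted every 2 days. The reminder names fever first among the symptoms to report, and the 5.1 bullets tell staff what to cover rather than giving patient-facing wording.

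Much of this stands. A reader might infer that the protocol permits or directs dosing through fever. It does not: no text says so, and the Infections text forbids it. A reader might count ten separate contradictions; there are three distinct texts, and the 4.5.3 bullet is weak evidence because of its heading. A reader might also want to express the gap as extra doses or added risk. The documents require immediate reporting but give no time to contact, so a dose count would rest on an assumed delay. It would not measure risk in any case, since Section 1.3 says that agranulocytosis is not dose-related within the therapeutic range. Nor can one say that patients are left uninstructed, because the consent form and emergency card are not shown and may already tell them to stop for fever.

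What does not fall away is the difference in wording. Compatibility with the Infections text helps a reader who has both texts in hand; the reminder is delivered to a patient who has not.

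**Conclusion.** The point holds as an inconsistency in a safety instruction. The stop clause in all eight visit reminders is narrower than the Infections text of 7.2.1.8 and the 4.5.3 sub-heading, and the mild-neutropenia paragraph can be read differently from the Infections text for a febrile patient with no identified infection. The consequence is confined mainly to the period before site contact, provided that patients report fever as told and sites apply 7.2.1.8. No endpoint, population, analysis or error rate is touched.

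Confidence is high that the wordings differ. It is lower that any patient would act differently, since that depends on materials outside the protocol and SAP. The correction is worth making because the self-stop message is part of the protocol's own case for reduced monitoring.

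**What to change.** In the eight reminders of Protocol 5.1 and the mild-neutropenia paragraph of 7.2.1.8.1, state: *interrupt deferiprone immediately if fever (>38.0 °C/100.4 °F, as in 4.5.3) or any type of infection develops*. For consistency, align the first bullet of 4.5.3 with its own heading. The temperature is the one that 4.5.3 already gives, so no new definition is needed. Check that the emergency card and other patient materials carry the same instruction, and amend them only if they do not.

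The cost is a few words in ten locations plus any matching patient material, with no new visit, test or analysis. The downside is a few more brief interruptions, which 7.2.1.8 already requires.

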5.2 Method of Assignment to Treatment

Not applicable. All patients in the extension study will receive deferiprone.

5.3 Blinding Procedures

Not applicable.

5.4 Allocation of Patient Numbers

All participants in study LA38-0411 will have been assigned a unique 6-digit number, where the first 3 digits represent the site code and the last 3 were sequentially assigned to each patient who signed the ICF. These assigned numbers will be maintained when patients continue on to study LA38-EXT.

Patients will be identified in all study data by this number rather than by name.

5.5 Treatment Compliance

Patients will be provided with a diary card in which they will daily record the number of Ferriprox tablets or volume of deferiprone oral solution taken. Compliance will be evaluated quarterly by the investigator or delegate by monthly pill counts or volume of drug returned. Reasons for non-compliance with the treatment will be recorded in the source document and in the eCRFs. The investigator should discuss treatment compliance with the patient at each visit.

Compliance reported in the eCRF will be based on the patient's diary and on the return of used and unused medication containers. If compliance is greater than 100% and the patient reports taking all doses as prescribed, compliance will be reported as 100% in the eCRF. Under-compliance < 80% and over-compliance >120% will be reported as a protocol deviation, unless under-compliance is due to treatment interruption because of infection or neutropenia or other extenuating circumstances (see Section 7.2.1.8).

6 STUDY TREATMENTS

All patients in the extension study will receive deferiprone.

6.1 Investigational Product

Deferiprone is manufactured by Apotex Inc., and will be supplied to the clinical sites by ApoPharma Inc.

6.1.1 Dosage Form and Mode of Administration

Deferiprone is provided as 500 mg film-coated scored tablets or 80 mg/mL oral solution. The tablets are marketed under the brand name Ferriprox[®]. Both forms are taken orally, 3 times a day.

6.1.2 Precautions for Use

Deferiprone can be taken with or without food, as per the investigator's recommendation.

6.2 Reference Product

Not applicable. All participants in study LA38-EXT will receive deferiprone.

6.3 Packaging and Labeling

Ferriprox tablets will be supplied in bottles of 100 tablets each, high-density polyethylene (HDPE) bottles with child-resistant closure. Deferiprone oral solution will be supplied in 250 mL bottles with child-resistant closure.

Both the tablet containers and oral solution containers will be provided with labels whose content is in accordance with all applicable regulatory requirements. The label will include protocol number, expiry date, lot/batch number, investigational statement, storage temperature, dosage, direction for use, visit number, date dispensed, and name and address of the sponsor.

6.4 Shipping and Storage

The study medication at each site will be kept in a secure location under adequate storage conditions, as per label requirements, with access to authorized individuals only. The room must have a calibrated digital temperature-monitoring device, and site personnel must use a temperature log to facilitate daily recording of the temperature of the storage facility. The site must report temperature deviations immediately to the sponsor, and quarantine the product until the sponsor deems it acceptable for use.

6.5 Product Accountability

Each site must maintain a record of inventory and a record of dispensing for the investigational product. Investigational product accountability lies with the investigator at all

times. The investigator must maintain an updated Site Investigational Drug Inventory Record at the study site. This log will include at a minimum:

- Name of sponsor
- Name of investigator
- Study identifier
- Date and quantity of investigational product received from sponsor
- Lot/batch number

For each patient, the investigator must maintain an updated Patient Investigational Drug Dispensing Record. This log will include at a minimum:

- Patient identification number
- Date of dispensing and return
- Dispenser's initials
- Quantity dispensed and returned

At the conclusion of the study, a final inventory must be performed by the investigator (or delegate). If any tablets or bottles are missing, this must be indicated on the study drug accountability form, together with an explanation of the discrepancy. These forms must be available for sponsor clinical monitoring as well as for sponsor audit and regulatory authority inspection purposes at any time.

It is the responsibility of the investigator to ensure that all study drug received at the study center is inventoried and accounted for throughout the study. Records of receipt, storage and administration of the study drug supplied must be maintained, and the drug accountability will be verified by the sponsor or sponsor's designee during on-site monitoring visits. At the conclusion of the study, a final inventory must be performed by the investigator or delegate. The sponsor will be responsible for determining the specific conditions for destruction of unused product.

6.6 Replacement Doses

Patients will be dispensed study medication at the start of the extension study and quarterly thereafter. Dispensing of study medication must be done by appropriately qualified staff (e.g., physician, pharmacist, or nurse).

Patients reporting that their medication has been lost or misplaced will be asked to attend the study site to receive replacement medication. Requests for replacement must be made in

writing by the appropriate clinical site member (pharmacist/physician/investigator) to the sponsor's Project Leader, Clinical Research, who will approve the request. All information related to the lost/misplaced medication and the replacement medication must be recorded in the drug accountability forms.

6.7 Disposition of Unused Product

All investigational product that has been returned by the patient or that is unused for any other reasons will be returned to the sponsor or discarded by the site according to internal procedures, which must include the issuance of appropriate signed destruction certificates including mode of destruction and complete drug accountability of destroyed materials.

6.8 Other Study Supplies

All required study supplies, including but not limited to diary cards and laboratory kits, will be provided to the sites.

